1.2 Secondary Objectives

- 1.2.1 To evaluate the efficacy of melatonin treatment on delayed sleep onset latency in long-term childhood cancer survivors.

Hypothesis 2

Long-term survivors of childhood cancer with delayed sleep onset latency at baseline (Cohorts 2 and 3), randomized to the melatonin treatment arm, will demonstrate improved sleep onset latency following six (6) months of treatment compared to the placebo groups.

- 1.2.2 To investigate whether improvement in sleep onset latency due to melatonin treatment is associated with neurocognitive improvement in long-term childhood cancer survivors.

Hypothesis 3

Improvement in sleep onset latency with melatonin treatment will result in improved neurocognitive performance in long-term childhood cancer survivors who have both comorbid delayed sleep onset latency and neurocognitive deficits at baseline (Cohort 2).

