Exogenous melatonin also has been demonstrated to promote sleep onset latency in healthy adult humans,⁴⁹ as well as adults with insomnia combined with dementia,⁵⁰ and mild cognitive impairment.⁴³ A meta-analysis on the efficacy of exogenous melatonin for primary insomnia reported reduced sleep onset latency of -7.2 minutes (95% CI -12.0 to -2.4).⁵¹ Efficacy has further been demonstrated in individuals with intellectual disabilities and autism spectrum disorder.⁵² Recent meta-

analyses of the effects of exogenous melatonin on sleep parameters reported decreased sleep latency of 23 and 34 minutes in individuals with delayed sleep phase disorder⁵³ and intellectual disabilities,⁵⁴ respectively. In a large randomized double blind placebo controlled trial, Wade and colleagues demonstrated significantly reduced sleep onset latency in adults 18-80 years of age over a six month trial, with a treatment effect of -6.8 minutes (95% CI -10.9 to -2.6).⁵⁵ Furthermore, their data demonstrated that treatment efficacy was independent of endogenous melatonin levels with no signs of tolerance or reduction in benefit during the 6-month treatment period.

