3.1 Inclusion Criteria

3.1.1 A St Jude Life participant who was previously treated at SJCRH.

3.1.2 Participant is 10 or more years from diagnosis.

3.1.3. Participant is ≥ 18 years of age.

3.1.4 Participant is able to speak and understand the English language.

3.1.5 Participant has a FSIQ score >79 .

3.1.6 Cohort 1 participant:

- a. Has neurocognitive impairment defined as performance on at least one measure of attention, memory, and/or executive functioning \leq 10th percentile.
- b. Is absent of delayed sleep onset latency defined as an inability to fall asleep within 30 minutes $<$ once a week during the past month.

Cohort 2 participant:

- a. Has neurocognitive impairment defined as performance on at least one measure of attention, memory, and/ or executive functioning \leq 10th percentile.
- b. Has delayed sleep onset latency defined as self-report of an inability to fall asleep within 30 minutes \geq once a week during the past month.

Cohort 3 participant:

- a. Is absent of neurocognitive impairment defined as performance $>$ 10th percentile on all six measures of attention, memory, and executive functioning.
- b. Has delayed sleep onset latency defined as self-report of an inability to fall asleep within 30 minutes \geq once a week during the past month.

3.1.7 Female participant of childbearing age must not be pregnant (confirmed by serum or urine pregnancy test within 1 week of eligibility) or lactating.

3.1.8 Female research participant of childbearing age and male research participant of child fathering potential must agree to use safe contraceptive methods.

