There are 10 subscales on which a survivor could be impaired and, out of 10 such subscales, we have identified six in which the marginal impairment rates were seen to be greater than 15%. There are normalized Z-scores available for each subscale and a survivor that falls below the 10% (≤ -1.3) is classified as impaired on that subscale. It is possible that a survivor could be impaired on more than one subscale but we will assess improvement in each subscale independently. Thus, we will have the Z-score corresponding to each of the subscales within at baseline and at follow-up visit. For simplicity, consider the first subscale. We don't expect to see any change in the Z-scores for the placebo arm but we do expect to see an improvement in the melatonin arm. Let Z_{1m}^1 and Z_{2m}^1 denote the Z-scores at baseline and follow-up time points for the first subscale on melatonin arm and let Z_{1p}^1 and Z_{2p}^1 denote the Z-scores at baseline and follow-up time points for the first subscale in the placebo arm. Let $Z_{DM}^1 = Z_{2m}^1 - Z_{1m}^1$ and $Z_{DP}^1 = Z_{2p}^1 - Z_{1p}^1$ denote the difference between the two time points in the two arms. Then our interest is in testing the null hypothesis $H_0: \mu_{Z_{DM}^1} = \mu_{Z_{DP}^1}$ vs $H_1: \mu_{Z_{DM}^1} \neq \mu_{Z_{DP}^1}$ i.e. the mean of the difference scores for the first subscale would be same for the two arms vs. they will be different. The lowest test-retest correlation coefficient for the neurocognitive measures has been observed to be 0.60. Then, assuming the difference in the Z-scores to be normally distributed but assuming (conservatively) the variance to be 1, we will need to randomize 131 survivors between the melatonin and placebo arm to detect an improvement of 0.66 units (in standardized scale, considered to be clinically meaningful) with 80% power with type I error control $\alpha=0.05/6=0.0083$ to adjust for multiplicity of 6 tests for each subscale. However, the sample size required to evaluate the secondary objective in cohorts 2 and 3 is 131 and 133, respectively, per cohort. Thus, we plan to enroll 131 research participants from Cohorts 1 and 2 and 133 research participants from Cohort 3.

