The primary interest of Objective 2 is to assess the efficacy of melatonin on delayed sleep onset latency in adult survivors of childhood cancer, which will be evaluated in Cohorts 2 and 3. We hypothesize that survivors randomized to the melatonin treatment arm will evidence a greater improvement in sleep onset latency compared to survivors randomized to placebo. The CCSS cohort mean and SD for sleep onset latency among participants with delayed sleep onset latency (i.e. $SOL \geq 30$ minutes) is 46.2 and 27.7 minutes, respectively. The test-retest correlation for sleep onset latency from the PSQI has been observed to be in the range of 0.70. Following the justification set forth in Aim 1, and assuming the SD to be 27.7, we will need to randomize 131 and 133 survivors between the melatonin and placebo arms in Cohort 2 and Cohort 3, respectively, to see an improvement of 15 minutes in sleep onset latency with 80% power with type I error control $\alpha=0.05$. The analysis for Aim 2 will be completed using a two-sample t-test.

Secondary Objective: Investigate whether improvement in sleep onset latency due to melatonin treatment is associated with neurocognitive improvement in long-term childhood cancer survivors.

- Hypothesis 3: Improvement in sleep onset latency with melatonin treatment will result in improved neurocognitive performance in long-term childhood cancer survivors who have both comorbid sleep onset latency and neurocognitive deficits at baseline (Cohort 2).

The secondary interest of Objective 2 is to investigate the association between

sleep onset latency and specific neurocognitive processes in survivors with comorbid sleep and neurocognitive dysfunction [Cohort 2]. We hypothesize that decreased sleep onset latency following 6 months of melatonin treatment will be associated with improved neurocognitive performance. With a sample size of 131 in Cohort 2 [66 randomized to melatonin, 65 randomized to placebo] we will have 80% power to detect a correlation of at least 0.25 between reduced sleep onset latency and improved neurocognitive performance with type 1 error control $\alpha=0.05$.

Exploratory Objective: Explore the association between endogenous melatonin levels and improvement in sleep onset latency.

- Exploratory Hypothesis 1: Improvement in sleep onset latency following melatonin treatment will be independent of baseline endogenous melatonin levels.

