11.2 Summary of Primary and Secondary Objectives

Primary and Secondary Summary of Objectives

Objective #	Objective Type	Analysis #	Resp Party	Stat	Safety	Analysis Measure	Analysis Title	Data Collection Time Frame	# of Participants
1.1	P	1	TB	KS	N	Patient Neurocognition	Compare neurocognitive function by treatment group	Baseline 6 month	232
2.1	S	1	TB	KS	N	Patient Sleep onset latency	Compare sleep onset latency by treatment group	Baseline 3 month 6 month	226
2.2	S	1	TB	KS	N	Patient Neurocognition and Sleep onset latency	Evaluate impact of sleep on neurocognitive function	Baseline 6 month	131
3.1	E	1	TB	KS	N	Patient Melatonin	Evaluate endogenous melatonin levels	Baseline 6 month	395
3.2	E	1	TB	KS	N	Patient Melatonin, Neurocognition Sleep onset latency	Evaluate association between endogenous melatonin and sleep	Baseline 6 month	395

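### Hypothesis 2 is one statement about Cohorts 2 and 3, but the plan sizes each cohort on its own, names no combined test and no rule for a split result, and its alpha, sample sizes and participant count disagree

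*Combined protocol and SAP*

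**What the plan says.** Section 1.2 states the hypothesis once, for "Long-term survivors of childhood cancer with delayed sleep onset latency at baseline (Cohorts 2 and 3), randomized to the melatonin treatment arm". Both cohorts enter on the same sleep criterion in section 3.1: "Has delayed sleep onset latency defined as self-report of an inability to fall asleep within 30 minutes", at least once a week over the past month. They receive the same product, are randomized 1:1 within cohort (section 3.6) and have the same endpoint. What separates them is cognitive status.

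Section 11.0 gives each cohort its own full size: "the sample size required to evaluate the secondary objective in cohorts 2 and 3 is 131 and 133, respectively, per cohort". Under Hypothesis 2 it says so again: "we will need to randomize 131 and 133 survivors between the melatonin and placebo arms in Cohort 2 and Cohort 3, respectively, to see" the target gain. That target is put as "to see an improvement of 15 minutes in sleep onset latency with 80% power". The error rate and the method are then given as "type I error control $\alpha=0.05$. The analysis for Aim 2 will be completed using a two-sample t-test". Secondary Aim 1 in the Protocol Summary repeats these figures. Row 2.1 of section 11.2 has one line, "Compare sleep onset latency by treatment group", with 226 participants.

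The 15 minutes is not justified in the text. Section 2.2.2 cites a placebo-controlled trial in adults, "over a six month trial, with a treatment effect of -6.8 minutes (95% CI -10.9 to -2.6", and a primary-insomnia meta-analysis at -7.2 minutes (-12.0 to -2.4). It also cites meta-analyses at 23 minutes (delayed sleep phase disorder) and 34 minutes (intellectual disability).

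**The concern.** The hypothesis is singular, but the sizing implies two separate tests. If one cohort is significant and the other is not, the plan does not say whether Hypothesis 2 is supported. If success in either cohort counts, the error rate depends on an alpha that the sample sizes do not confirm. If both must succeed, power is well below the stated 80% per cohort. Two half-size tests also give up precision on the question as posed, and the 15-minute target is about twice the effect in the two cited primary-insomnia sources (15/6.8 = 2.2; 15/7.2 = 2.1). At stake is a secondary objective that may end with an uninterpretable split, or miss a moderate effect that the same participants could detect in one test.

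**Working it through.** **Inputs.** Section 11.0: difference 15 min, SD 27.7, power 80%, alpha 0.05, N = 131 and 133, retest correlation 0.70. Section 3.6: 1:1 allocation. Section 2.2.2: 6.8 min. Two-sidedness is taken from the primary aim, whose justification this aim follows. I treat 131 and 133 as evaluable: the Protocol Summary asks for outcome data on that many, while section 11.0 speaks of randomizing them. Combined figures assume a common effect and SD. The 10-minute effect is my illustration.

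**1. The plan's own figure.** Normal approximation: n per arm = 2(z₁₋α/₂ + z₀.₈₀)²(SD/δ)².
- Alpha 0.05: 2(1.960 + 0.842)²(27.7/15)² = 53.5, so 54 per arm. The t-test needs 54.5, so 55 per arm, or 110.
- Alpha 0.025: 2(2.241 + 0.842)²(27.7/15)² = 64.8, so 65 per arm. The t-test needs 66.1 per arm, 132.2 in total, so 133.

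The stated 131/133 are not reproduced at alpha 0.05. At 0.05 they give 86.8% and 87.3% power at 15 minutes; at 0.025 they give 79.6% and 80.3%. The primary aim shows the same pattern: for 0.66 SD units, the stated 0.05/6 needs a total of 114.7 (116 with equal arms), while 0.05/12 needs 130.3, so 131.

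**2. Section 11.2.** 131 + 133 = 264, not 226. The unsplit alphas would give 116 + 110 = 226, so the row may be a leftover from smaller sizes. That is inference.

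**3. Separate against combined** (noncentral t, two-sided 0.05; SD of change from the retest correlation: 27.7 × √(2 × 0.30) = 21.5).

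| | Cohort 2 (131) | Cohort 3 (133) | Combined (264) |
|---|---|---|---|
| Detectable at 80%, SD 27.7 | 13.7 min | 13.6 min | 9.6 min |
| Detectable at 80%, SD 21.5 | 10.6 min | 10.5 min | 7.4 min |
| Power at 10 min, SD 27.7 | 53.6% | 54.2% | 83.2% |
| Power at 6.8 min, SD 27.7 | 28.6% | 29.0% | 51.1% |
| Power at 6.8 min, SD 21.5 | 43.7% | 44.2% | 72.8% |

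**4. Outcomes of two separate tests at 0.05, SD 27.7.**
- True effect 10 min: both significant 0.536 × 0.542 = 29%; neither 0.464 × 0.458 = 21%; exactly one 100 − 29 − 21 = 50%.
- True effect 6.8 min: both 0.286 × 0.290 = 8%; neither 0.714 × 0.710 = 51%; exactly one 41%. At SD 21.5, neither is 0.563 × 0.558 = 31%.
- No effect: at least one significant 1 − 0.95² = 9.75%.

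**The case against.** **Separate testing is not written for this aim.** Section 11.0 says the evaluation is independent by cohort only for the primary objective, and section 11.2 has a single row. That is fair. But two full per-cohort sizes have no other natural reading, and if one test was meant, the plan neither says so nor sizes it.

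**Combining gains little over an either-cohort rule.** At 6.8 minutes, at least one cohort is significant with probability 49%, against 51% combined (68% to 69% against 73% at SD 21.5). This stands, but only with 0.05 spent in each cohort. At 0.025 each, the either-cohort figure at 6.8 minutes and SD 27.7 falls to 36%. The plan states neither rule.

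**The error rate may already be controlled.** The sizes fit a split alpha of 0.025. If that was the intention, the 9.75% does not apply, though per-cohort power at 6.8 minutes drops to about 20%. The printed alpha is 0.05, so a reader cannot tell.

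**A common effect is assumed.** Cited effects range from about 7 to 34 minutes across populations, and no survivor data exist. The IQ floor (above 79) makes the intellectual-disability figure a poor analogue, but equal effects in the two cohorts are not shown. This is why cohort estimates should be kept.

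**The 15 minutes is defensible.** It lies within the cited range, and the 6.8-minute trial used 2 mg in primary insomnia. It is also a sizing assumption, not a threshold that the result must reach. This stands: what can be said is that the choice is unexplained, not that it is refuted.

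**Conclusion.** Three things hold. The plan names no combined test and no rule for a split result for a hypothesis stated over both cohorts. Its alpha of 0.05 does not agree with 131/133 at 80% power. Row 2.1 shows 226 against 264. A cohort-stratified test answers the stated question once and lowers the detectable difference by about 4 minutes (13.6 to 9.6) at SD 27.7. Its gain over a single-cohort test matters most for true effects of about 9.6 to 13.6 minutes, or 7.4 to 10.5 at SD 21.5, where the combined test reaches 80% power and a single cohort does not.

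Three stronger inferences are not supported. A reader might infer that combining would settle the question at the cited 6.8 minutes; with 51% power (73% at SD 21.5) it would not. A reader might infer that both cohorts would then probably miss; the chance is 51% at SD 27.7 and about 31% at SD 21.5. A reader might take 9.75% as the plan's false-positive rate; it applies only if either cohort suffices and the printed alpha is the one used.

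The figures rest on two-sided tests, 264 evaluable participants, and a common SD and effect. For a secondary objective this should be changed, but it does not threaten the trial.

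**What to change.** In section 11.0 and in Secondary Aim 1 of the Protocol Summary:
- Make the main test of Hypothesis 2 one between-arm comparison of 6-month change in sleep onset latency in Cohorts 2 and 3 combined, with cohort (the randomization stratum) as a term, at two-sided 0.05.
- Report each cohort's estimate with its confidence interval, and the arm-by-cohort interaction, as supportive.
- State the combined detectable difference (about 9.6 min at SD 27.7; 7.4 at SD 21.5) and the power at 6.8 min (about 51%; 73%), and give the reason for 15 minutes.
- Restate the alpha or the power behind 131/133 so that they agree: about 87% at 0.05, or about 80% at 0.025 per cohort.

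In section 11.2, change 226 to 264 in row 2.1.

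The cost is wording in these places, with no added participants or visits. Cohort 3's 133 was derived from the cohort-specific test, so the text should say that the sizes are kept for the combined test. The downside is dilution if only one cohort benefits; the cohort estimates and the interaction are there to show it, although the interaction test will have limited power.

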Secondary Aim 1: The primary interest of secondary aim one is to assess the efficacy of melatonin on delayed sleep onset latency in adult survivors of childhood cancer, which will be evaluated in Cohorts 2 and 3. We hypothesize that survivors randomized to the melatonin treatment arm will evidence a greater reduction in sleep onset latency compared to survivors randomized to placebo. The CCSS cohort mean and SD for sleep onset latency among participants with delayed sleep onset latency (i.e. SOL \geq 30 minutes) is 46.2 and 27.7 minutes, respectively. The test-retest correlation for sleep onset latency from the PSQI has been observed to be in the range of 0.70. Following the justification set forth in the Primary Aim, and assuming the SD to be 27.7, we will need outcome data for 131 survivors in Cohort 2 and 133 in Cohort 3 between the melatonin and placebo arms for these Cohorts to see an improvement of 15 minutes in sleep onset latency with 80% power with type I error control $\alpha=0.05$. The analysis for Aim 2 will be completed using a two-sample t-test.

Secondary Aim 2: The aim of this objective is to investigate the association between sleep onset latency and specific neurocognitive processes [Cohort 2]. We hypothesize that decreased sleep onset latency following 6 months of melatonin treatment will be associated with improved neurocognitive performance. We will need outcome data for 131 survivors in Cohort 2 [66 randomized to melatonin, 65 randomized to placebo] so that we will have 80% power to detect a correlation of at least 0.25 between reduced sleep onset latency and improved neurocognitive performance with type 1 error control $\alpha=0.05$.

Exploratory Aims: To explore the association between endogenous melatonin levels and improvement in sleep onset latency. To explore the association between sleep quality and psychological distress and health related quality of life.

Primary Anticipated Completion Date: [REDACTED]

Anticipated Study Completion Date: [REDACTED]

Timeframe for Primary Outcome Measure: Approximately 6 months

Data Management: Data will be managed by the Neuropsychology Research Team and the Clinical and Survey Research Center in the Department of Epidemiology and Cancer Control and the Department of Nursing Research. Statistical analysis will be provided by the Biostatistics Department at St. Jude Children's Research Hospital.

Human Subjects:

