2.2 Rationale

Research on childhood cancer survivors has reached a critical juncture where a shift from characterization of late effects to remediation of these deficits is necessary. Toward this aim, this study proposes the novel use of melatonin to intervene on two distinct, yet highly interrelated late effects of childhood cancer. This extends the traditional conceptualization of melatonin as a hormone that promotes sleep onset to one with the additive benefit of enhancing neurocognition.

2.2.1 Melatonin and neurocognition: Cognitive dysfunction is one of the most common late effects following treatment with CNS directed therapies for childhood cancer. While the pathogenesis of radiation-induced cognitive decline is not well understood, recent evidence suggests that disruption of hippocampal neurogenesis may be involved.³² Additionally, oxidative stress has been identified as a potential biological mechanism for CNS injury and predictor of neurocognitive dysfunction in survivors of childhood leukemia.^{33,34} Importantly, Manda et al³⁵ reported that treatment with melatonin protected against cranial irradiation induced inhibition of hippocampal neurogenesis by reducing oxidative stress in mice. Specifically, melatonin was found to reduce neuronal damage by scavenging free radicals and activating antioxidative enzymes³⁶ and

mounting evidence from animal models indicates that melatonin enhances neurocognitive function through its strong anti-inflammatory and anti-oxidant properties. Taken together, these lines of research provide a framework for understanding the potential mechanisms by which melatonin may address the delayed neurocognitive effects of cranial radiation therapy in childhood cancer survivors.

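### Hypothesis 3 rests on a correlation power statement across both arms with no arm term; read as a pooled correlation, it would mix any sleep–cognition link with melatonin's separate effects on each variable

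*Combined protocol and SAP*

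**What the plan says.** Secondary objective 1.2.2 asks whether "improvement in sleep onset latency due to melatonin treatment is associated with neurocognitive improvement". Hypothesis 3 states it causally and confines it to Cohort 2, whose members have both problems at baseline.

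On analysis, section 11.0 offers only this: "With a sample size of 131 in Cohort 2 [66 randomized to melatonin, 65 randomized to placebo] we will have 80% power". The target is a correlation of 0.25 or more, and alpha is 0.05. Secondary Aim 2 in the Protocol Summary repeats it ("80% power to detect a correlation of at least 0.25 between reduced sleep onset latency and improved neurocognitive performance"). The table in section 11.2 adds a title and the number 131.

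Other aims do get a named method. The Protocol Summary names a two-sample t-test for the primary aim and for the sleep-latency aim, and section 11.0 names regression for the exploratory objectives. None of this extends to Hypothesis 3.

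Three other statements bear on the point:
- Section 11.0 expects no change in Z-scores on placebo, but "we do expect to see an improvement in the melatonin arm". The trial is sized for a 0.66-unit difference.
- Section 11.0 sizes the sleep objective for a 15-minute difference in latency.
- Section 2.2.1 reports animal evidence that "melatonin enhances neurocognitive function through its strong anti-inflammatory and anti-oxidant properties", a route to cognition that need not pass through sleep.

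**The concern.** The two drug effects, on cognition and on latency, are already tested between arms under Hypotheses 1 and 2. What Hypothesis 3 can add is whether people whose latency improves more also improve more in cognition. A correlation over both arms without an arm term cannot separate that from two parallel drug effects. If melatonin moves both variables, the melatonin group sits higher on both and the placebo group lower on both, and the pooled scatter slopes upward whatever happens inside each group. A positive result would therefore be ambiguous exactly when the drug works.

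**Working it through.** **Inputs (section 11.0).** Arms of 66 and 65; target correlation 0.25; alpha 0.05 (sidedness is not stated for this test; two-sided assumed). Cognition: difference 0.66, SD of change 1, lowest test-retest correlation 0.60. Latency: difference 15 minutes, SD 27.7, test-retest correlation about 0.70. For a smaller latency effect I take 7 minutes, because section 2.2.2 cites 6.8 and 7.2 minutes in insomnia. That section also cites 23 and 34 minutes in other populations.

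**1. The plan's power figure.** Fisher z: power = Φ(atanh(r)·√(N−3) − 1.960).
- All 131: 0.2554 × √128 = 2.890, power 82.4%. For exactly 80%, N = ((1.960 + 0.842)/0.2554)² + 3 = 123.3, so 124. The stated 80% is met with a little to spare.
- Melatonin arm alone (66): 0.2554 × √63 = 2.027, power 52.7%. The statement therefore needs both arms.
- All 131 with an arm term, 0.25 taken as the partial correlation: 0.2554 × √127 = 2.878, power 82.1%. This also meets 80%, so the figure does not show which analysis was intended.

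**2. Correlation induced by pooling when the within-arm link is zero.** Let q = (66/131)(65/131) = 0.250, and let d₁ and d₂ be the drug effects on cognition and latency in within-arm SDs. The pooled covariance is q·d₁·d₂ and each pooled variance is 1 + q·d², so

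r = q·d₁·d₂ / √[(1 + q·d₁²)(1 + q·d₂²)].

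Two sets of SDs are used. The planning SDs are 1 and 27.7. Those implied by the test-retest correlations are √(2(1−0.60)) = 0.894 and 27.7·√(2(1−0.70)) = 21.46.

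| SDs | Latency effect | d₁ | d₂ | Induced r | Pooled test rejects (nominal 5%) |
|---|---|---|---|---|---|
| Planning | 15 min | 0.660 | 0.542 | 0.0893/1.091 = 0.082 | 15.3% |
| Test-retest | 15 min | 0.738 | 0.699 | 0.1290/1.129 = 0.114 | 25.4% |
| Planning | 7 min | 0.660 | 0.253 | 0.039 | 7.3% |
| Test-retest | 7 min | 0.738 | 0.326 | 0.056 | 9.7% |

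First row in full: atanh(0.082) × √128 = 0.929, and Φ(0.929 − 1.960) + Φ(−0.929 − 1.960) = 15.3%.

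Simulation of 40,000 trials per row gave 15.4%, 25.5%, 7.2% and 9.8% for the pooled test. The arm-adjusted test gave 4.9%, 5.1%, 4.9% and 4.8%.

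**3. What the arm term costs if 0.25 was meant as the pooled correlation.** With the full 0.66 and 15-minute effects, the within-arm correlation behind a pooled 0.25 is 0.25·√[(1 + q·d₁²)(1 + q·d₂²)] − q·d₁·d₂.
- Planning SDs: 0.25 × 1.091 − 0.0893 = 0.183; arm-adjusted power 55%.
- Test-retest SDs: 0.25 × 1.129 − 0.129 = 0.153; arm-adjusted power 41%.

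**The case against.** **The plan never says it will pool without adjustment.** This is right. A reader might infer that the sponsor has chosen an unadjusted pooled correlation, but the documents do not support that: it is the literal reading of a power sentence, and an arm-adjusted analysis fits the same sentence. The inflation describes what happens if the literal reading is followed.

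**The 15–25% is the full-effect case.** Also right. It needs both differences fully realised and exactly no link within arms. The 0.66 and 15 minutes are differences the trial is sized to detect, not forecasts. Section 11.0's alternative analysis assumes that 12% against 5% improve on a subscale. With normal changes of equal SD, that is 1.645 − 1.175 = 0.47 SD, which gives an induced r of 0.06–0.08 and rejection of 10–14% at 15 minutes, or 6–7% at 7 minutes. The pilot in section 2.3.2 also found longer latency associated with poorer long-term memory, so some real link is plausible.

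**An arm term does not test the stated objective either.** The objective concerns latency improvement due to melatonin. Conditioning on arm removes the latency shift that randomisation produces and leaves variation within arms, including spontaneous change on placebo. If melatonin works through sleep, part of what is removed is signal. A single arm term also assumes the same slope in both arms. This stands as a limit on interpretation. It does not rescue the pooled correlation, which cannot tell that signal from parallel effects.

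**Multiplicity.** Because section 11.0 says "we will assess improvement in each subscale independently", a reader might infer that Hypothesis 3 should be judged at the primary aim's 0.05/6 and is underpowered there. The plan does not support this: both the Protocol Summary and section 11.0 set alpha at 0.05 for this aim.

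**Conclusion.** The point holds as a modest, worthwhile improvement to a secondary aim. The plan leaves the Hypothesis 3 analysis unstated, and its literal reading would let melatonin's separate effects on latency and cognition pass for a link between them. The induced correlation is 0.08–0.11 at the full planned differences and 0.04–0.06 at 7 minutes, in both cases well below the 0.25 target. Rejection is 15–25% and 7–10% respectively, against about 5% with an arm term. These figures assume normal changes with equal variances in the two arms, no within-arm link, and a drug effect on both outcomes. If melatonin leaves either variable unchanged, the artefact disappears.

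Two stronger conclusions should be avoided. The 80% power statement is not wrong, since two-sided power is 82.4%. Nor can one say without qualification that the 80% survives adjustment: that is true only if 0.25 is defined as the arm-adjusted correlation.

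**What to change.** In section 11.0 and in Secondary Aim 2 of the Protocol Summary:

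1. State the analysis: regress change in cognition on change in sleep onset latency, with treatment arm as a covariate, in all 131 Cohort 2 participants. Adding the two baseline values is optional.
2. State that the 0.25 target is the arm-adjusted (partial) correlation.
3. Add one sentence of interpretation: the result is a within-arm association and does not by itself show that latency improvement due to melatonin causes cognitive improvement.

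Alpha stays at 0.05. No new data or participants are needed. Under the definition in item 2, power moves from 82.4% to 82.1% (81.5% with both baselines), so the stated 80% holds. The downside to name is that, if the sponsor meant 0.25 as the pooled correlation, arm-adjusted power at the full planned effects is about 41–55%, and the plan should say so.
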